10.2.4 Treatment-Emergent Adverse Events per Patient-Years of Exposure

TEAEs will be summarized by event rate per 100 subject years, defined as

$$100 \times \frac{\text{Number of TEAEs}}{\text{Total Patient Years}}$$

where total patient years is defined as the sum of the study drug exposure of all subjects, normalized by 365.25, and rounded to 1 decimal place. Note that one event per preferred term per day per subject will be counted in the calculation of the number of AEs (i.e., a preferred term will not be counted twice on the same day for the same subject).

The TEAE rates per 100 patient-years of exposure will be provided for each AE category in the AE overview summary (defined in Section 10.2.2) and for TEAE summary by SOC and PT.

The study drug exposure for each safety population is defined in the table below.

Safety Population	Scenario	Study Drug Exposure Definition
SA1, SA2	Enrolls in Study M14-430 or Part 3 at the end of Part 1/Part 2	Last dose date in Part 1/Part 2 - 1 st dose date in Part 1/Part 2 + 1
	Does not participate in the Study M14-430 or Part 3	
SA3	Enrolls in Study M14-430	Last dose date in Part 3 - 1 st dose date in Part 3 + 1
	Does not participate in the Study M14-430	
SA4	Enrolls in Study M14-430	Last dose date in Study M14-431 - 1 st dose date in Part 1/Part 2 + 1
	Does not participate in the Study M14-430	
SA-UPA	Enrolls in Study M14-430	Last dose date of upadacitinib in Study M14-431 - 1 st dose date in upadacitinib in M14-431 + 1
	Does not participate in the Study M14-430	

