6.0 Study Drug Duration and Compliance

For the safety populations (SA1, SA2 and SA3), duration of treatment will be summarized for each treatment group for Part 1 (SA1), for overall for Part 2 (SA2) and for each cohort for Part 3 (SA3). Duration of treatment is defined for each subject as last dose date minus first dose date + 1. Duration of treatment will be summarized for each treatment group using the number of subjects treated, mean, standard deviation, median, minimum, and maximum. In addition, the number and percentage of subjects in each treatment duration interval (≥ 2 weeks, ≥ 4 weeks, ≥ 6 weeks, ≥ 8 weeks, ≥ 10 weeks, ≥ 12 weeks) will be summarized.

Treatment compliance will be summarized by treatment group in Part 1, for overall in Part 2 and by cohort in Part 3. Treatment compliance is defined as the number of tablets actually taken divided by the number of tablets that should have been taken. Percent compliance will be summarized.

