10.2.1 Treatment-Emergent Adverse Events

Part 1 (SA1 population) /Part 2 (SA2 population): TEAEs for Part 1/Part 2 are defined as events that begin either on or after the first dose of the study drug in Part 1/Part 2 and until (i) the first dose of study drug in the Study M14-430 (if applicable), or (ii) until first dose of study drug in Part 3 (if applicable), or (iii) within 30 days after the last dose administration of the study drug in Part 1/Part 2, whichever is earlier.

Part 3 (SA3 population): TEAEs for Part 3 are defined as events that begin either on or after the first dose of the study medication in the Part 3 and until (i) first dose of study drug in the Study M14-430 (if applicable), or (ii) within 30 days after the last dose of the study drug in the Part 3, whichever is earlier.

All Upadacitinib (SA-UPA population): TEAEs for "All Upadacitinib" are defined as events that begin either on or after the first dose of upadacitinib and (i) until first dose of study drug in the Study M14-430 (if applicable), or (ii) within 30 days after the last dose of upadacitinib in the study, whichever is earlier.

24-Week Upadacitinib (SA4 population): TEAEs for "24-Week Upadacitinib" (SA4) are defined as events that begin either on or after the first dose of upadacitinib and until (i) first dose of study drug in the Study M14-430 (if applicable), or (ii) within 30 days after the last dose of upadacitinib in the study, whichever is earlier.

If an incomplete onset date was collected for an adverse event, the event will be assumed to be treatment-emergent unless there is other evidence that confirms that the event was not treatment-emergent (e.g., the event end date was prior to the study drug start date). The number and percentage of subjects experiencing treatment-emergent AEs will be summarized. For Part 1, the risk difference and 95% CI between upadacitinib group and placebo group will be presented.

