10.2.2 Adverse Event Overview

An overview of AEs will be presented consisting of the number and percentage of subjects experiencing at least one event for each of the following AE categories:

- Any TEAE
- Any TEAE related to COVID-19
- Any TEAE that was rated as related to study drug by the investigator.
- Any severe TEAE
- Any serious TEAE.
- Any TEAE leading to discontinuation of study drug.
- Any TEAE leading to death.
- Treatment-emergent AESI ([Appendix B](#)).
- All deaths
 - Deaths occurring \leq 30 days after last dose of study drug
 - Deaths occurring $>$ 30 days after last dose of study drug
 - Deaths related to COVID-19

In addition, an overview of AEs per 100 patient-years of study exposure will be presented for the AE categories defined above. The number of TEAEs reported, the total number of years of study drug exposure, and the TEAE rate per 100 patient-years will be presented.

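### Adverse event rates per 100 patient-years count events up to 30 days after the last dose but stop person-time at the last dose, so they are biased upward, more in Part 3 than in Parts 1 and 2

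*SAP*

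**What the plan says.** **Numerator.** SAP 10.2.1 opens the treatment-emergent window at first dose. For Parts 1 and 2 it closes at the first dose in Study M14-430, "until first dose of study drug in Part 3 (if applicable"), or "within 30 days after the last dose administration of the study drug in Part 1/Part 2, whichever is earlier". For Part 3 it closes at the first M14-430 dose or "within 30 days after the last dose of the study drug in the Part 3, whichever is earlier". SA4 and SA-UPA follow the same pattern, counted from the last upadacitinib dose.

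**Denominator.** SAP 10.2.4 defines total patient-years by the sentence "where total patient years is defined as the sum of the study drug exposure of all subjects, normalized by 365.25" and refers to a table for exposure by population. For SA1 and SA2 the entry is "Last dose date in Part 1/Part 2 - 1 st dose date in Part 1/Part 2 + 1"; for SA3 it is "Last dose date in Part 3 - 1 st dose date in Part 3 + 1". SA4 and SA-UPA use the same last-minus-first construction. No days after the last dose are added anywhere.

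**Supporting text.** SAP 10.2.2 says that, with the event count, "the total number of years of study drug exposure, and the TEAE rate per 100 patient-years will be presented". SAP 6.0 builds treatment duration in the same way: "Duration of treatment is defined for each subject as last dose date minus first dose date + 1".

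The rates are reported by treatment group (SAP 10.1), for the overview categories and by system organ class and preferred term (SAP 10.2.4), and for the adverse events of special interest (SAP 10.2.6 and Table B-2).

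**The concern.** A rate needs events and person-time from the same window. Here the windows agree for a subject who moves straight into the next study period, because the event window closes at the next first dose. They disagree for a subject who leaves: up to 30 further days of events are counted and none of those days enters the denominator.

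The mismatch therefore depends on who continues, and the design makes that differ by part. After Part 1 or 2, clinical responders may enter M14-430 and non-responders may enter Part 3 (Protocol 5.1), so nearly every completer has somewhere to go. After Part 3, Week 24 non-responders are discontinued and have a follow-up visit 30 days after last dose. A reader who compares 12-week SA1 rates with SA3, SA4 or SA-UPA rates would see differences produced partly by the arithmetic.

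**Working it through.** The documents state no adverse event rate, patient-year total or non-continuation share, so there is no planned figure to reproduce.

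**Inputs from the documents**
- Post-dose window: 30 days (SAP 10.2.1).
- Planned exposure: 84 days in each part (12 weeks, Protocol 5.1); 168 days for SA4 (24 weeks).
- Part 1 arm sizes: 330 and 165 (Protocol 8.3).
- The last dose of each period is taken the day before the Week 12 or Week 24 visit (Protocol 5.1), so the gap is about a day if the next study drug starts at that visit.

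**Assumptions**
- *f*, the share not continuing: 5-30% for Parts 1 and 2, 30-70% for Part 3.
- *dn*, mean exposure of those subjects: 42 days in Parts 1 and 2; full exposure (84 or 168 days) for SA3 and SA4.
- Constant event rate and a fully observed 30 days.

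**Direction.** Let E_on and E_off be events up to and after the last dose, and T_on and T_off the matching times. The SAP rate is (E_on + E_off)/T_on. It cannot be lower than (E_on + E_off)/(T_on + T_off), the time-at-risk rate, or than E_on/T_on, the on-treatment rate.

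**One subject who does not continue:** (d + 30)/d.
- d = 84: 114/84 = 1.36
- d = 28: 58/28 = 2.07
- d = 14: 44/14 = 3.14

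A subject who continues the next day has a ratio of about 1.00.

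**A group:** inflation = 1 + 30f / [(1 − f) × 84 + f × dn].

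| Population | f | Calculation | Inflation |
|---|---|---|---|
| Part 1/2 | 5% | 1 + 1.5/81.9 | 1.02 |
| Part 1/2 | 10% | 1 + 3/79.8 | 1.04 |
| Part 1/2 | 20% | 1 + 6/75.6 | 1.08 |
| Part 1/2 | 30% | 1 + 9/71.4 | 1.13 |
| Part 3 | 30% | 1 + 9/84 | 1.11 |
| Part 3 | 50% | 1 + 15/84 | 1.18 |
| Part 3 | 70% | 1 + 21/84 | 1.25 |
| SA4 (168 days) | 30% | 1 + 9/168 | 1.05 |
| SA4 (168 days) | 50% | 1 + 15/168 | 1.09 |
| SA4 (168 days) | 70% | 1 + 21/168 | 1.13 |

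**Sensitivity to the constant-rate assumption.** Compared with the on-treatment rate, if events after last dose occur at half or at twice the on-drug rate, the excess at f = 20% in Part 1/2 is 4% or 16%. At f = 50% in Part 3 it is 9% or 36%.

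**Part 1 rate ratio, upadacitinib over placebo.** The distortion is the inflation in one arm divided by that in the other.
- 5% in both arms, same dn: 1.00
- 5% vs 10%: 1.018/1.038 = 0.98
- 5% vs 20%: 1.018/1.079 = 0.94
- 10% vs 30%: 1.038/1.126 = 0.92

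**Worked example.** Assume a true rate of 300 per 100 patient-years in both arms, f = 5% (upadacitinib) and 20% (placebo), dn = 42.
- Exposure: 330 × 81.9/365.25 = 74.0 and 165 × 75.6/365.25 = 34.2 patient-years.
- Time at risk: 75.4 and 36.9 patient-years.
- Expected events: 226.1 and 110.6.
- SAP rates: 305.5 and 323.4, a false ratio of about 0.94.

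**The case against.** **The table.** The mismatch concerns only subjects who do not continue, and the exposure-table rows for them show no entry of their own. The sentence above defers to that table, so it cannot settle the matter alone. A merged cell is the natural reading and agrees with SAP 10.2.2 and 6.0, but it should be confirmed in the original layout. This caveat stands.

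**Size in Parts 1 and 2.** A reader might take the 36% for a non-continuing completer as the error in the Part 1 rates. The documents do not support that: the earlier-of rule removes the excess for everyone who continues, and the group effect is probably a few percent.

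**Arms.** A reader might infer that the rates are biased between upadacitinib and placebo. No document gives continuation by arm, and both responders and non-responders have a next step after Week 12. The assumed range for the rate ratio includes no distortion. The Part 1 comparison stated in SAP 10.2.1 is a risk difference in the proportion of subjects with events, which uses no person-time.

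**Follow-up after the last dose.** It may be a single visit or a telephone call, and after withdrawal of consent it depends on willingness (Protocol 5.1). Fewer events may be captured then, which would reduce the excess relative to an on-treatment rate. It also means that a denominator of last dose plus 30 days, without censoring, would overcorrect.

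**Labelling.** The SAP says openly that the denominator is study drug exposure. That is transparent, but it does not align the windows.

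**Conclusion.** The point holds, subject to confirming the table layout. The direction is certain: the specified rates equal or exceed a rate with matched windows. The denominator is calendar days from first to last dose, interruptions included, and it ends too early for the events being counted.

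The size rests on assumed non-continuation: about 2-8% in Parts 1 and 2 at 5-20%, and about 11-25% in Part 3 at 30-70%, with a constant event rate. The difference between parts follows from the design. It is enough that SA1, SA3, SA4 and SA-UPA rates should not be read side by side as they stand. A difference between the Part 1 arms is conditional: the rate ratio is multiplied by about 0.92 to 1.00 over the range examined.

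Two further inferences are not supported. The Part 1 risk difference is not affected. Nor is it shown that every column of Table B-2 shares the fault: SAP 10.2.4 defines an event rate only and gives no denominator for the exposure-adjusted incidence rate.

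**What to change.** In SAP 10.2.4, define person-time for these rates as first dose to the earliest of:
- last dose plus 30 days;
- first dose in Part 3 (SA1 and SA2 only);
- first dose in Study M14-430;
- death;
- end of follow-up.

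For SA-UPA, the start and the last dose refer to upadacitinib, as in SAP 10.2.1. Alternatively, keep the present denominator and restrict the rate numerator to events starting on or before the last dose; later events would still appear in the counts and percentages.

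Apply the same rule to the exposure-adjusted event rate column of Table B-2. Complete the exposure table explicitly for subjects who do not continue.

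The cost is SAP wording and one more derived variable. Rates will be equal to or lower than under the present rule, and no other planned safety analysis changes.

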10.2.5 SAEs (Including Deaths) and Adverse Events Leading to Study Drug Discontinuation

SAEs (including deaths) and AEs leading to study drug discontinuation will be summarized by SOC and PT and in listing format.

10.2.6 Adverse Events of Special Interest

The AESI categories will be identified by the search criteria per Standard MedDRA Queries (SMQs)/Company MedDRA Queries (CMQs) specified in [Appendix B](#).

Treatment-emergent AESIs will be summarized by SOC and PT and listing format. Additionally, AESI rates per 100 patient years of exposure will be provided for each AESI category ([Appendix B](#)) in the AE overview summary.

10.3 Analysis of Laboratory Data

Data collected from central and local laboratories, including additional laboratory testing due to an SAE, will be used in all analyses, except for baseline where SAE-related laboratory assessments on or before the first dose of study drug will be excluded. The clinical laboratory tests defined in the protocol (e.g., hematology and clinical chemistry) will be summarized.

Analysis of Quantitative Laboratory Parameters

Each laboratory variable will be summarized for all time points (starting at baseline) with the number of non-missing observations, mean, standard deviation, median, minimum and maximum. Mean change from Baseline to each applicable post-baseline visit will be summarized for selected laboratory variables, with the number of observations, baseline mean, and visit mean. The change from baseline mean, standard error, and 95% CI will be presented for the mean change from Baseline within each treatment group.

For SA1 population, treatment group differences between upadacitinib group and placebo group for changes from baseline will be analyzed using a one-way Analysis of Variance (ANOVA) model with treatment as a fixed factor and 95% CI for treatment difference will be presented for selected laboratory parameters.

Shift Table Analyses

Changes in laboratory parameters will be tabulated using shift tables categorized as low, normal, or high based on the normal ranges of the laboratory used for each sample. A shift table from baseline to minimum and maximum value (based on normal range) will be created. A similar shift table will be provided to summarize shifts from baseline to the final post-baseline value.

Potentially Clinically Significant Laboratory Values

The criteria for potentially clinically significant laboratory values will be determined by CTCAE criteria of Grade 3, Grade 4 and \geq Grade 3, with a grade worsening compared to baseline. Toxicity grading scale is based on National Cancer Institute Common Toxicity Criteria (NCI CTC) AE version 4.03. The number and percentage of subjects meeting the criteria for potentially clinically significant laboratory values will be summarized by treatment group. Listings of subject-level laboratory data will be provided for subjects meeting the criteria.

Assessment of Liver Elevations

The liver-specific laboratory tests include the serum glutamic pyruvic transaminase (SGPT/ALT), serum glutamic-oxaloacetic transaminase (SGOT/AST), alkaline phosphatase (ALP), and total bilirubin (TBL). The frequencies and percentages of subjects with post baseline liver specific function test values that meet the following criteria of potential clinical interest will be summarized by treatment group:

- ALT > 3 × ULN
- ALT > 5 × ULN
- ALT > 10 × ULN
- ALT > 20 × ULN
- AST > 3 × ULN
- AST > 5 × ULN

- $AST > 10 \times ULN$
- $AST > 20 \times ULN$
- $TBL > 2 \times ULN$
- $ALP > 1.5 \times ULN$
- $ALT \text{ and/or } AST > 3 \times ULN \text{ and } TBL > 1.5 \times ULN$
- $ALT \text{ and/or } AST > 3 \times ULN \text{ and } TBL > 2 \times ULN$

where ULN is the upper normal limit. The maximum ratio relative to the ULN will be used to determine if subjects meet any of the criteria listed above.

A listing of possible Hy's Law cases, defined as those meeting the following criteria will also be provided:

- $ALT \text{ and/or } AST > 3 \times ULN \text{ and } TBL > 1.5 \times ULN$

In addition, eDISH plots will be created displaying post-baseline total bilirubin versus post-baseline ALT, in terms of the maximum ratio relative to the ULN (not necessarily concurrent).

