**Statistical Methods (Continued):**

**Pharmacokinetic:** A non-linear mixed-effects modeling approach will be used to estimate the population central values and the empirical Bayesian estimates of the individual values for upadacitinib oral clearance and volume of distribution. Additional parameters may be estimated if useful in the interpretation of the data. Data from this study may be combined with data from other studies for the population pharmacokinetic analyses.

**Safety:** AEs, laboratory data, and vital signs are the primary safety parameters in this study. All safety comparisons will be performed between treatment groups using the safety set. Treatment-emergent AEs are defined as events that begin or worsen either on or after the first dose of the study drug and within 30 days after the last dose of the study drug for subjects who do not participate in Study M14-430, or within 30 days after the last dose of study drug in Study M14-431 or first dose of study drug in Study M14-430 if the subject enrolls in Study M14-430, whichever comes first.

An overview of treatment-emergent AEs, including AEs of special interest, AEs leading to death, AEs leading to PD, AEs by Medical Dictionary for Drug Regulatory Activities preferred term and system organ class, AEs by maximum relationship to study drug, and AEs by maximum severity will be summarized by number and percentage.

Changes in laboratory data will be described using statistical characteristics and comparison between treatment groups will be performed using a one-way Analysis of Variance. In addition, shift tables and listings will be provided for abnormal values, whereby the normal range of the analyzing laboratory will be used. Vital signs will be analyzed similarly.

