#### **8.1.7 Safety Analyses**

Safety analyses will be performed on safety analysis sets (Part 1, Part 2 and Part 3), as defined in Section 8.1.1.2. Incidence of AEs, changes in vital signs, physical examination results, and clinical laboratory data will be assessed throughout the study. ECGs will be performed at screening and at the end of each Part 1, 2, 3 of the study. AEs and laboratory data when available will be graded as described in the NCI CTCAE, and summarized accordingly.

AEs will be coded using the Medical Dictionary for Regulatory Activities (MedDRA). Treatment-emergent AEs are defined as events that begin or worsen either on or after the first dose of the study drug and within 30 days after the last dose of the study drug for subjects who do not participate in Study M14-430, or within 30 days after the last dose of the study drug in Study M14-431 or first dose of study drug in Study M14-430 if the subject enrolls in Study M14-430, whichever comes first.

An overview of treatment-emergent AEs, including AEs leading to death, AEs leading to premature discontinuation, AEs by MedDRA preferred term and system organ class, AEs by maximum relationship to study drug, AEs by maximum severity and AEs of special interest will be summarized by number and percentage.

Changes from Baseline in continuous laboratory and vital sign parameters will be summarized by treatment group. Treatment group differences between upadacitinib and placebo groups for changes from Baseline may be analyzed using a one-way ANOVA. Vital signs and laboratory data will be described by statistical characteristics and frequency of abnormal values. In addition, shift tables and listings will be provided for abnormal values, whereby the normal range of the analyzing laboratory will be used. Analysis details will be specified in the SAP.

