10.4 Analysis of Vital Signs

Vital sign measurements of systolic and diastolic blood pressure, pulse rate, body weight, respiratory rate and body temperature will be summarized.

Each vital sign variable will be summarized for all time points (starting with Baseline) with the number of non-missing observations, mean and standard deviation, median, minimum and maximum. Mean change from Baseline to each applicable post-baseline visit will be summarized for each vital sign variable, with the number of observations, Baseline mean, and visit mean. The change from Baseline mean, standard error, and 95% CI will be presented for the mean change from Baseline within each treatment group.

For SA1 population, treatment group differences between upadacitinib group and placebo group for changes from Baseline will be analyzed using a one-way Analysis of Variance

(ANOVA) with treatment as a fixed factor and 95% CI for treatment difference will be presented for each vital sign variable.

Vital sign variables will be evaluated based on potentially clinically important (PCI) criteria ([Appendix C](#)). For each vital sign PCI criterion, the number and percentage of subjects who have a vital sign value meeting the criteria will be summarized. Listings will be provided to summarize subject-level vital sign data for subjects meeting PCI criteria.

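### The Part 1 between-arm intervals for laboratory and vital-sign change leave out the baseline value; adding it would usually narrow them at almost no cost

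*SAP*

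**What the plan says.** SAP 10.3 compares the Part 1 arms on laboratory change from baseline with a model in which treatment is the only term: changes "will be analyzed using a one-way Analysis of Variance (ANOVA) model with treatment as a fixed factor and 95% CI for treatment difference". The scope is limited: "95% CI for treatment difference will be presented for selected laboratory parameters". SAP 10.4 says of vital signs that "changes from Baseline will be analyzed using a one-way Analysis of Variance", and covers all of them: "ANOVA) with treatment as a fixed factor and 95% CI for treatment difference will be presented for each vital sign variable". Both apply to the Part 1 safety population, SA1.

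The protocol names the same model with different force. Section 8.1.7 is permissive: "Treatment group differences between upadacitinib and placebo groups for changes from Baseline may be analyzed using a one-way ANOVA". The Statistical Methods part of the synopsis is firm for laboratory data: "comparison between treatment groups will be performed using a one-way Analysis of Variance". It adds that vital signs are handled in a similar way.

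Three other places bear on the point:
- SAP 10.1 defines the Part 1 baseline for these measurements as the last one available before study drug.
- SAP 9.2.2 includes the baseline measurement in both the MMRM and the ANCOVA for continuous efficacy endpoints.
- SAP 10.2.1 gives a safety interval that does not come from the ANOVA: "For Part 1, the risk difference and 95% CI between upadacitinib group and placebo group will be presented".

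Neither document says why the safety model leaves baseline out.

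**The concern.** A change score subtracts the whole baseline value, which amounts to fixing at 1 the slope of the visit value on baseline. When the true slope is below 1, change is negatively correlated with baseline. Part of the variation between subjects is then predictable from a value already in the database, and a one-way ANOVA leaves that part in the residual. A chance difference between arms at baseline also carries into the estimate.

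The parameters matter. Protocol 3.2 reports higher transaminases, lipids and CPK, and lower haemoglobin and white cells, with upadacitinib. Protocol 5.6.4 justifies the dose partly by limiting laboratory effects. Only Part 1 is randomised against placebo, so these contrasts are the study's randomised estimates of mean laboratory and vital-sign shift. A wider interval describes such a shift less precisely.

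**Working it through.** The documents give no SD, correlation, interval width or power for these comparisons, so there is no stated figure to reproduce.

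**Inputs.** From protocol 8.3: 330 subjects on upadacitinib and 165 on placebo. Assumed: r, the correlation between baseline and the visit value, and k, the SD at the visit divided by the baseline SD s. A slope common to both arms is also assumed.

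**Formulas.**
- Residual variance, one-way ANOVA on change: s²(1 + k² − 2rk).
- Residual variance, ANCOVA with baseline: s²k²(1 − r²).
- The first minus the second is s²(1 − rk)². It is never negative, and it is zero when the slope rk equals 1.
- With k = 1, the variance ratio ANCOVA/ANOVA is 2(1 − r)(1 + r)/2 ÷ 2(1 − r) = (1 + r)/2, so the width ratio is √((1 + r)/2).
- Standard-error factor: √(1/165 + 1/330) = 0.0953. The 95% half-width is 1.96 × 0.0953 × the residual SD.

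**Equal SDs (k = 1), half-widths in baseline-SD units.**

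| r (assumed) | ANOVA on change | ANCOVA | Narrower by |
|---|---|---|---|
| 0.3 | 0.2211 | 0.1783 | 19.4% |
| 0.5 | 0.1869 | 0.1618 | 13.4% |
| 0.7 | 0.1448 | 0.1335 | 7.8% |
| 0.8 | 0.1182 | 0.1121 | 5.1% |
| 0.9 | 0.0836 | 0.0815 | 2.5% |
| 0.95 | 0.0591 | 0.0584 | 1.3% |

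For example, at r = 0.5 the ANOVA residual SD is √(2 × 0.5) = 1 and the ANCOVA residual SD is √(1 − 0.25) = 0.866.

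**Unequal SDs.** At r = 0.7 and k = 0.8 the variances are 0.52 and 0.3264, so the interval is 20.8% narrower. At r = 0.7 and k = 1.25 they are 0.8125 and 0.7969, a gain of 1.0%. At r = 0.8 and k = 1.25 the slope is 1 and the gain is nil.

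**Validity.** Six settings of r and k were simulated at 330 and 165, with normal data, no treatment effect and 4,000 trials each. Coverage was 94.5% to 95.7% for both methods. At r = 0.8, k = 1.25 the mean half-widths were 0.1403 (ANOVA) and 0.1405 (ANCOVA).

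**Chance imbalance.** Given an observed baseline difference d, the change-score contrast is shifted by (rk − 1)d. Take r = 0.5, k = 1 and d at 1.96 standard errors: 1.96 × 0.0953 = 0.187 SD. The shift is 0.5 × 0.187 = 0.093 SD in size, half the ANOVA half-width. A difference at least that large, in either direction, is expected for about 1 parameter in 20. ANCOVA removes the shift under the common-slope assumption.

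**The case against.** The planned comparison is unbiased over randomisations, has correct coverage, and is named in both documents. No safety hypothesis, margin or alpha depends on it. A difference from the efficacy models is not a contradiction, because those serve controlled tests and this serves a safety summary. All of that stands.

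The gain is uncertain, and this stands too. The screening limits on transaminases, haemoglobin, neutrophils and lymphocytes restrict the baseline spread, and a drug effect may enlarge the later spread. Both could push k above 1, and the slope may then lie close to 1. At high correlations the gain is small even with equal SDs.

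A change score already subtracts baseline, so imbalance is not ignored altogether. That is true, but it is corrected with a slope fixed at 1, and the shift above remains whenever the slope differs from 1.

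A reader might infer that every safety interval is widened. The documents do not support that. Adverse-event risk differences and within-arm intervals for mean change do not use this contrast, and laboratory contrasts cover selected parameters only. Nor are these intervals the only randomised safety evidence: shift tables, toxicity-grade counts, liver criteria, vital-sign criteria and events of special interest are also summarised by arm without the ANOVA.

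**Conclusion.** The point holds as a minor matter of efficiency. The Part 1 between-arm intervals for selected laboratory parameters and for each vital sign omit a baseline value that the trial already collects, with no reason stated. With equal SDs, adjustment would narrow them by about 19%, 13%, 8% and 3% at correlations of 0.3, 0.5, 0.7 and 0.9, and by nothing at slope 1. The size rests on assumed r and k and on a slope common to both arms. The ratios do not depend on the sample size, apart from one degree of freedom.

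It might also be inferred that the planned intervals are wrong. They are not: they have correct coverage, and no decision rule in the plan turns on them.

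**What to change.** - In SAP 10.3 and 10.4, replace the one-way ANOVA with ANCOVA on change from baseline, with treatment as factor and the same parameter's baseline as covariate. Report the adjusted difference and its 95% CI.
- Align protocol 8.1.7 and the Statistical Methods text of the synopsis. The permissive wording of 8.1.7 would not block the SAP change, but the firm wording of the synopsis would conflict with it.

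The cost is one covariate in the model statement and the matching text edits. No new data, visits or analysis set are needed. No subject is lost, since a change score already requires a baseline value.
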